**Pregnancy Outcomes According to Cervical Cerclage
Indications and Factors Affecting Pregnancy Duration and
Outcomes: A 2-Year Comparison Of Patients Who
Underwent History-Based, Ultrasound-Based, or Rescue
Cerclage**

.....Hospital Clinical Research Ethics Committee (ethics no.2023-605, date: 22.11.2023)

Study Protocol

This study retrospectively reviewed data from pregnant women who underwent cerclage from July 2021 to July 2023 in Hospital, which is a perinatal medical center in Istanbul, Turkey. The local ethics committee approved the study.

All procedures followed the relevant guidelines and regulations of the institutional ethics review board and the Declaration of Helsinki.

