The patients were divided into three subgroups for data analysis. Group 1 included patients with history-indicated cerclage, who had second-trimester pregnancy loss associated with painless cervical dilatation in the absence of labor or placental abruption, or previous cerclage due to painless cervical dilatation in the second trimester. Group 2 comprised patients with ultrasound-indicated cerclage, who had a history of spontaneous preterm birth before the 34th week previously and their cervical length was <25 mm before the 24th week of gestation in the current singleton pregnancy, or who had <10 mm cervical length in the current singleton pregnancy without history. Group 3 consisted of patients undergoing rescue cerclage, who had premature cervical dilatation and exposure of fetal membranes in the vagina, was detected in ultrasound or speculum examination of the cervix. All cervical cerclage procedures were performed by a senior obstetrician using the McDonald technique with Mersilene tape or No:1 proline. We collected the following data from medical records: maternal age at cervical cerclage, gravidity, parity, body mass index, history of a cervical cone biopsy, history of premature birth and cervical cerclage, procalcitonin level, C-reactive protein (CRP) level, gestational age at cerclage, pre-and post-cerclage cervical length (CL), week of birth, pregnancy complications (preterm premature rupture of the membranes (PPROM), abruptio placenta, chorioamnionitis). We defined successful cerclage as postponing birth until after the 28th week of gestation and a 'good outcome' was defined as delivery beyond 34 completed weeks. We reviewed the indications and the pregnancy outcomes (miscarriage, gestational age at delivery, birth weight, prolongation of pregnancy, and rate of preterm birth before 34 weeks) of cervical cerclage and analyzed the factors associated with successful cervical cerclage in our perinatal medical center.

Moreover, receiver operating characteristic (ROC) curves were used to calculate the pre-cerclage and post-cerclage CL cut-off value required to predict if birth could be postponed birth until after the 28th week of gestation in women with cervical insufficiency (CI). Thus, we

extracted significant factors for a successful cervical cerclage for long-term pregnancy sustenance in women with CI.

Statistical Analysis Plan

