All data were analyzed using the statistical software package SAS version 15.2 (SAS Institute Inc.). The Kolmogorov-Smirnov test was used to test the normality assumption. The three groups of patients were compared in terms of three outcomes, successful cerclage, good outcomes, and PPROM. For categorical variables, a comparison among the three groups of patients regarding socio-demographics and clinical features was conducted using the Chi-square or Fisher's exact test, as appropriate. For continuous variables, the three groups of patients were compared using the Kruskal-Wallis test or analysis of variance (ANOVA), as appropriate. Within each group, we compared the patients in terms of successful cerclage, good outcomes, and PPROM. A p-value less than 0.05 was considered statistically significant. The predictive power of pre- and post-operation cervix length in identifying successful cerclage was evaluated using receiver operating characteristic (ROC) curves, and the area under the curve (AUC) determined the discriminative ability of the parameters. The optimal cut-off values are derived using Youden's Index.

Results

We included 129 patients with a singleton pregnancies in this study. Three membrane rupture complications occurred during the cervical cerclage procedure (all three cases were in the emergency cerclage group and the pouches were prolapsed). Externally, no uncontrollable bleeding or injury to the bladder and/or rectum occurred during cerclage. The sample size was 129 patients, with 32 in the history-indicated cerclage group (G1), 62 in the ultrasound-indicated cerclage group (G2), and 35 in rescue cerclage group (G3). Only six (4.6%) pregnancies resulted in miscarriage before 20 weeks of gestation. Among these three groups, significant differences were observed in gravidity, parity, history of preterm birth, and history of CI. In group 1, the average gravidity was 4.69 (2.05), whereas in groups 2 and 3, it was much lower at 2.47 (1.83) and 2.23 (3.81), respectively. Similarly, parity was much higher in group 1 than in groups 2 and 3.

We compared the three groups in terms of factors that could affect cervical cerclage success and pregnancy outcomes of cerclage cases. Among these three groups, significant

differences were observed in cerclage week, the time elapsed from cerclage to childbirth, post-operation cervix length, complication rates, successful cerclage and good outcomes (delivery beyond 34 completed weeks).

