The average cerclage week was 14.39 (1.99) in group 1, but the week of cerclage performance was later in groups 2 and 3 (21.47 (2.97) and 20.98 (4.14), respectively).

The average time elapsed from cerclage to childbirth was much longer in group 1, with an average of 143.63 (41.27) days, whereas it was relatively shorter in group 2, with an average of 94.46 (35.16) days. The shortest time elapsed from cerclage to birth was observed in group 3, with an average of 69.82 (49.35) days.

In groups 1 and 2, the percentage of patients with successful cerclage was much higher (90.6% and 88.7%, respectively) than in group 3 (66.7%). Similarly the percentage of patients with good outcomes was much higher for the patients in groups 1 and 2 in comparison with group 3. The earlier cerclage is applied after CI is identified, the longer the time from cerclage to birth.

We also evaluated the effects of preop cervical length, postop cervical length, preop procalcitonin value, preop CRP, cerclage week, and cerclage material on cerclage results for each group separately. Within group 1, we compared the patients who had successful cerclage with the patients who did not in terms of pre-op cx, post-op cx, procalcitonin, CRP, the week of cerclage, and the material of cerclage. We found significant difference in these two groups in terms of the average procalcitonin; however, we only had three patients with unsuccessful cerclage and all three patients had the same procalcitonin values. Therefore, we did not report the p-value for this comparison. Based on this result, although we cannot clearly say that high procalcitonin values reduce cerclage success in the prophylactic cerclage group, the effects of procalcitonin need to be studied on cerclage success in more detail.

In the prophylactic cerclage group, there was also a significant difference between patients with and without PPROM ($p<.0001$). The average post-operation cervix length for patients without PPROM was 34.5 (4.64) mm, whereas the average post-operation cervix length for patients with PPROM was 19.4 (0.85) mm. We concluded that the longer the postoperative cervix length, the lower the probability of PPROM in the prophylactic cerclage group.

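### The miscarriage figure before 20 weeks (6/129) counts women whose cerclage came at or after 20 weeks, so read as a risk of early loss after cerclage it is too low

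*Combined protocol and SAP*

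**What the plan says.** The Study Protocol describes a cohort assembled from hospital records: it "retrospectively reviewed data from pregnant women who underwent cerclage from July 2021 to July 2023". Miscarriage heads its list of pregnancy outcomes: "We reviewed the indications and the pregnancy outcomes (miscarriage, gestational age at delivery".

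The first paragraph of the Results gives the cohort size ("We included 129 patients with a singleton pregnancies in this study") and the split ("32 in the history-indicated cerclage group (G1), 62 in the ultrasound-indicated cerclage group (G2), and 35 in rescue cerclage group (G3"). It then reports early loss in one sentence: "Only six (4.6%) pregnancies resulted in miscarriage before 20 weeks of gestation".

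Further on, the Results give the timing of the procedure by group: "The average cerclage week was 14.39 (1.99) in group 1", whereas "the week of cerclage performance was later in groups 2 and 3 (21.47 (2.97) and 20.98 (4.14), respectively".

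The documents do not state how many women had their cerclage before 20 weeks, how the six miscarriages divide between the groups, or that the denominator was limited to women who could have the event.

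**The concern.** A pregnancy must be ongoing when the cerclage is placed. A woman treated at 21 or 22 weeks has therefore already passed the period in which the event is counted. She can add to the denominator but never to the numerator. Both groups with a mean cerclage week above 20 are in the denominator in full, and they make up 97 of 129 women (75%).

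At stake is how a listed outcome is read. With 'Only' in front, 4.6% suggests that early loss after cerclage is rare. Part of that low figure comes from women who were never at risk of it. The share at risk also differs sharply by indication: almost all of group 1, but probably a minority of groups 2 and 3. A single pooled percentage therefore describes none of the three groups.

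**Working it through.** **Inputs (all from the Results).** Six miscarriages before 20 weeks. Group sizes 32, 62 and 35, total 129. Cerclage week 14.39 (1.99), 21.47 (2.97) and 20.98 (4.14); the bracketed values are taken to be standard deviations.

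**Step 1: reproduce the printed figure.** 6/129 = 4.65%. Truncated to one decimal this is the printed 4.6%; rounded it is 4.7%. The denominator is the full cohort. The exact 95% CI is 1.7% to 9.8%.

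**Step 2: estimate the number at risk, assuming normality.** The share treated before 20 weeks is Φ((20 − mean)/SD).

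| Group | n | (20 − mean)/SD | Share before 20 weeks | Women at risk |
|---|---|---|---|---|
| 1 | 32 | (20 − 14.39)/1.99 = 2.82 | 0.998 | 31.9 |
| 2 | 62 | (20 − 21.47)/2.97 = −0.49 | 0.310 | 19.2 |
| 3 | 35 | (20 − 20.98)/4.14 = −0.24 | 0.406 | 14.2 |
| All | 129 | | | 65.4 |

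About 63.6 women (49%) are then estimated to have been treated after 20 weeks.

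**Step 3: proportion among women at risk.** 6/65.4 = 9.2%. The exact 95% CI for 6/65 is 3.5% to 19.0%. The printed figure is 4.65/9.18 = 0.51 of this estimate.

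**Step 4: vary the assumption.**

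| Shape of cerclage week | Women at risk | 6 / at risk |
|---|---|---|
| Normal, cut-off 19.5 weeks | 60.2 | 10.0% |
| Normal, cut-off 20.5 weeks | 70.9 | 8.5% |
| Lognormal | 67.5 | 8.9% |
| Uniform | 69.2 | 8.7% |
| Pearson III, skew −1 | 60.7 | 9.9% |
| Pearson III, skew +1 | 70.0 | 8.6% |

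**Step 5: limit without any assumed shape.** By Cantelli's inequality, the largest possible share before 20 weeks in a group whose mean exceeds 20 is SD²/(SD² + (mean − 20)²).

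- Group 2: 8.82/(8.82 + 2.16) = 0.803, or 49.8 of 62.
- Group 3: 17.14/(17.14 + 0.96) = 0.947, or 33.1 of 35.
- With all 32 of group 1, at most about 114.9 women were at risk, and 6/114.9 = 5.2%.

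So at least about 14 of the 129 were treated at or after 20 weeks whatever the shape. The direction of the understatement is settled; its size is not.

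**The case against.** The strongest reply is that the sentence is true as written. It reports six pregnancies and their share of the cohort. It does not call the figure a risk, an incidence or a failure rate. The Statistical Analysis Plan compares the groups on successful cerclage, good outcome and PPROM, not on miscarriage, and no test or conclusion rests on the 4.6%. Births too early to count as success, which include these losses, already lower the success rates of 90.6%, 88.7% and 66.7%, so the reader can see that early failure is not rare in group 3. All of this stands, and it makes the point one of reporting. It does not rescue the figure as a measure of early loss after treatment, which is how 'Only' asks the reader to take it.

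The second reply is that the number at risk is inferred. That also stands. Means and standard deviations do not fix the count, and the plan itself does not take normality for granted: it tests for it and allows Kruskal-Wallis.

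Three stronger readings are tempting, and the documents do not support them.

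- **That the printed rate is a miscalculation.** It is a correct cohort share. The difference between 4.6% and 4.7% is truncation and has no consequence.
- **That 4.6% is half the true risk.** The 9.2% is modelled, rests on six events and has a wide interval. It also counts a woman treated at 19 weeks the same as one treated at 13.
- **That groups 2 and 3 must have a rate of 9% or more.** Group 1 had only three unsuccessful cerclages, so at least three of the six losses do lie in groups 2 and 3. But the 33 or so women at risk there (19.2 + 14.2) are a modelled number. With 40 at risk, 3/40 = 7.5%. An estimated denominator cannot give a floor.

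**Conclusion.** The point holds as a matter of reporting. The printed 4.6% includes women who could not have the event, so as a risk of early loss after cerclage it is too low. That direction follows from entry at cerclage and from group means above 20 weeks, without any assumption about shape.

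The size is an estimate. If cerclage week is roughly normal within groups, about 65 of 129 women were at risk and the proportion is about 9% (exact 95% CI about 3.5% to 19%). Other plausible shapes give 8.6% to 9.9%; the distribution-free extreme is 5.2%. The interval reflects only the sampling error of six events, not the uncertainty in the denominator.

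Even with the right count the proportion stays crude. Women treated shortly before 20 weeks had little time at risk, so it still understates the risk for a woman treated early. The group comparisons of success, good outcome and PPROM do not depend on this figure.

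**What to change.** From the records already collected (gestational age at cerclage and week of birth):

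1. Report, for each group and overall, the actual number of women whose cerclage was placed before 20 weeks and the number of miscarriages before 20 weeks among them, with exact 95% CIs.
2. State that women treated at or after 20 weeks are not at risk of this outcome and are left out of its denominator.
3. Drop 'Only', or keep 6/129 and label it as a share of the whole cohort, printed as 4.7%.
4. Note that time at risk was short for women treated just before 20 weeks. A time-to-event estimate with delayed entry at cerclage would handle this, but with six events it is an optional refinement.

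The cost is one re-tabulation and a few sentences, with no new data. The resulting figure will be less favourable and less precise than the one printed.

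### The rescue-group success rate of 66.7% cannot come from the 35 women stated for that group, and no n/N is given

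*Combined protocol and SAP*

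**What the plan says.** The Study Protocol section makes success a yes/no outcome: "We defined successful cerclage as postponing birth until after the 28th week of gestation". The Statistical Analysis Plan section makes it one of three outcomes for the group comparison: "The three groups of patients were compared in terms of three outcomes, successful cerclage, good outcomes, and PPROM".

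The Results section gives the sample as 129 women, "with 32 in the history-indicated cerclage group (G1), 62 in the ultrasound-indicated cerclage group (G2), and 35 in rescue cerclage group (G3"). It later gives the success rates by group: the percentage in groups 1 and 2 "was much higher (90.6% and 88.7%, respectively) than in group 3 (66.7" per cent). None of the three rates is printed with a numerator and denominator. The only count of successes or failures is for group 1, where "we only had three patients with unsuccessful cerclage".

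The text reports no exclusion, missing birth outcome or loss to follow-up in group 3. It does report three membrane ruptures during the procedure: "all three cases were in the emergency cerclage group and the pouches were prolapsed".

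**The concern.** A binary outcome in 35 women must have a whole-number numerator, so its rate can take only 36 values. The printed 66.7% is not one of them. The stated group size and the stated rate therefore cannot both describe the same 35 women.

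There are two possible causes. One is a wrong digit, which is minor. The other is that some rescue-group women were left out of the outcome denominator without being mentioned. That would matter more, because this is a retrospective record review that lists week of birth among the data collected, and the reader would not know whose outcome is missing or why. At stake is the rate of a named outcome in the highest-risk group, and the only outcome percentage printed for that group.

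**Working it through.** **Inputs** (all from the Results section): group sizes 32, 62 and 35; success rates 90.6%, 88.7% and 66.7%; three failures in group 1; three membrane ruptures in the emergency group, taken here to be group 3.

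**Step 1. Group sizes.** 32 + 62 + 35 = 129, which agrees with the stated total.

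**Step 2. Reproduce the two rates that should work.**
- Group 1: 32 − 3 = 29 successes; 29/32 = 90.625%, printed as 90.6%.
- Group 2: 55/62 = 88.71%, printed as 88.7%. The neighbours 54/62 = 87.10% and 56/62 = 90.32% do not fit.

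Both rates use the full stated group.

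**Step 3. Group 3 on 35 women.** 22/35 = 62.86%, 23/35 = 65.71%, 24/35 = 68.57%. None gives 66.7%, rounded or truncated.

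**Step 4. Smaller denominators.**
- 34: 22/34 = 64.71%, 23/34 = 67.65%. Neither fits.
- 33: 22/33 = 66.67%. Fits.
- 32 (dropping the three membrane ruptures): 21/32 = 65.62%, 22/32 = 68.75%. Neither fits.
- 31: 20/31 = 64.52%, 21/31 = 67.74%. Neither fits.
- 30: 20/30 = 66.67%. Fits.

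So 33 is the nearest smaller denominator that fits, and 30 is the next.

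**Step 5. Range on all 35 women if 22/33 was observed.** Two outcomes would be missing. If both were failures, 22/35 = 62.9%; if both were successes, 24/35 = 68.6%. Against the printed figure that is 66.7 − 62.9 = 3.8 points lower, or 68.6 − 66.7 = 1.9 points higher.

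**Step 6. Effect on the three-group test.** Pearson chi-square (2 df) and Fisher's exact test by full enumeration, with group 1 at 29/32 and group 2 at 55/62. As an example, with 23/35 there are 3 + 7 + 12 = 22 failures among 129 women. The expected failures are 32 × 22/129 = 5.46, 62 × 22/129 = 10.57 and 35 × 22/129 = 5.97, and summing (O − E)²/E over all six cells gives 10.14.

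| Group 3 | Rate | Chi-square | p | Smallest expected count | Fisher p |
|---|---|---|---|---|---|
| 23/35 | 65.7% | 10.14 | 0.0063 | 5.46 | 0.0095 |
| 22/33 | 66.7% | 9.17 | 0.0102 | 5.29 | 0.0164 |
| 22/35 | 62.9% | 12.28 | 0.0022 | 5.71 | 0.0042 |
| 24/35 | 68.6% | 8.15 | 0.0170 | 5.21 | 0.0273 |

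Every expected count is above 5, and both tests are below 0.05 in each of these readings.

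**The case against.** The strongest reply accepts the arithmetic and disputes its weight. A single wrong digit (65.7 printed as 66.7) is the simplest explanation and moves the rate by one point. The Results print no p-value for the three-group comparison of success, only that the difference was significant, and that survives 65.7%, 66.7% or 68.6%. The ROC analysis is reported for group 2 only. The text is a prose summary, and fuller tables may exist elsewhere. All of this is fair and limits the point to a correction of the report. It does not remove the conflict, because a table elsewhere would not make 66.7% a possible rate in 35 women.

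A second reply cuts the other way: the size limits above depend on 22/33, and 20/30 fits equally well as arithmetic. In that case five outcomes would be missing, and success on all 35 could run from 20/35 = 57.1% to 25/35 = 71.4%. At 25/35 the chi-square p is 0.042 with a smallest expected count of 4.96, and Fisher's exact p is 0.060. This stands as a caveat. Five unreported omissions, all of them successes, is an extreme case, but the documents do not exclude it.

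It is tempting to settle the denominator from the mean time from cerclage to birth. If days were whole numbers, 69.82 is possible with 33 women (2304/33) or 34 (2374/34) but not with 35. The same test fails in group 2: 94.46 days does not fit 62 women, although the success rate there does. That check is given no weight.

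**Conclusion.** The concern holds. The printed rate is either wrong or based on an undisclosed subset, and the documents cannot say which. If it is a misprint of 65.7%, the correction is about one point. If 22/33 was observed, the rate on all 35 women is at most 3.8 points lower or 1.9 points higher than printed. Under both readings the direction and significance of the group difference are unchanged, and no printed p-value is contradicted. These limits assume that groups 1 and 2 are 29/32 and 55/62, and that no more than two women were left out of group 3. With five left out, the limits widen as described above. This should be corrected, but it does not overturn the reported comparison.

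**What to change.** Check the 35 group 3 records against the recorded week of birth and restate successful cerclage as n/N on all 35 women. If any woman's outcome is truly unknown, report the actual denominator, the number missing and the reason. Correct the percentage and rerun the three-group test on the corrected counts, using Fisher's exact test if an expected count falls below 5.

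The cost is a review of 35 existing records, one restated percentage and one rerun test. No new data are needed.

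### The Results conclude that earlier cerclage gives a longer time to birth, but that interval starts at cerclage, and the gap between groups 1 and 2 matches their difference in placement week

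*Combined protocol and SAP*

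**What the plan says.** The Study Protocol section lists among the data collected "gestational age at cerclage, pre-and post-cerclage cervical length (CL), week of birth", and among the pregnancy outcomes "miscarriage, gestational age at delivery, birth weight, prolongation of pregnancy, and rate of preterm birth before 34 weeks". It defines the three groups by indication: history (32 patients), ultrasound (62) and rescue (35). The Statistical Analysis Plan provides ANOVA or Kruskal-Wallis tests for continuous variables across the groups. It describes no analysis relating cerclage week to timing of birth.

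The Results report:

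- **Placement:** "The average cerclage week was 14.39 (1.99) in group 1, but the week of cerclage performance was later in groups 2 and 3", at 21.47 (2.97) and 20.98 (4.14) weeks.
- **Interval, group 1:** "The average time elapsed from cerclage to childbirth was much longer in group 1, with an average of 143.63 (41.27) days".
- **Interval, group 2:** "whereas it was relatively shorter in group 2, with an average of 94.46 (35.16) days".
- **Interval, group 3:** "The shortest time elapsed from cerclage to birth was observed in group 3, with an average of 69.82 (49.35) days".

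After the comparison of successful cerclage (90.6%, 88.7% and 66.7%) and good outcome comes the conclusion: "The earlier cerclage is applied after CI is identified, the longer the time from cerclage to birth". The Results text gives no group values for week of birth.

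**The concern.** For each patient, the interval is gestational age at birth minus gestational age at cerclage. The exposure, placement week, is therefore subtracted inside the outcome. Earlier placement lengthens the interval even if every birth stays where it is, so the sentence would hold with no effect of timing at all.

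Because it follows directly on the success and good-outcome results, it can be read as evidence that earlier placement prolongs pregnancy. The between-group contrast cannot supply that evidence. The groups differ by indication, and the Results report differences in gravidity, parity and obstetric history. The sentence also speaks of timing after cervical insufficiency is identified, but no time from identification to cerclage is listed as collected or reported.

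**Working it through.** **Inputs** (Results), mean (SD):

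| Group | n | Cerclage week | Interval, days |
|---|---|---|---|
| 1 | 32 | 14.39 (1.99) | 143.63 (41.27) |
| 2 | 62 | 21.47 (2.97) | 94.46 (35.16) |
| 3 | 35 | 20.98 (4.14) | 69.82 (49.35) |

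The means cannot be regenerated without patient data. The success rates of groups 1 and 2 do reproduce from whole counts: 29/32 = 90.6% and 55/62 = 88.7%.

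**Step 1. Implied mean birth week** = cerclage week + interval/7, assuming both means cover the same patients.

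- Group 1: 14.39 + 143.63/7 = 34.91
- Group 2: 21.47 + 94.46/7 = 34.96
- Group 3: 20.98 + 69.82/7 = 30.95

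**Step 2. Group 1 against group 2** (Welch 95% CIs).

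- Interval: 143.63 - 94.46 = 49.17 days longer in group 1 (32.0 to 66.3)
- Placement: (21.47 - 14.39) x 7 = 49.56 days earlier in group 1 (42.4 to 56.7)
- Remainder: 49.17 - 49.56 = -0.39 days, or -0.06 weeks of gestation at birth
- Success: 90.6% - 88.7% = 1.9 percentage points (Newcombe 95% CI -14.0 to 13.8)

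**Step 3. The other contrasts.**

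- Group 3 minus group 2: placement (20.98 - 21.47) x 7 = -3.4 days (-14.6 to 7.7); interval 69.82 - 94.46 = -24.6 days (-43.6 to -5.7). Placement week does not explain that gap. This does not show a reversed effect.
- Group 1 minus group 3: interval gap 143.63 - 69.82 = 73.81 days. Placement accounts for (20.98 - 14.39) x 7 = 46.13 days; 27.68 days remain as a difference in birth week, confounded with indication.

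**Step 4. Uncertainty on the birth-week differences.** The birth-week SD, in weeks, is sqrt(SD_C² + SD_I² + 2·r·SD_C·SD_I), where C is cerclage week, I is the interval and r is their within-group correlation. r is not reported, so it is varied by assumption:

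| Difference, weeks | r = -0.8 | r = 0 | r = +0.5 |
|---|---|---|---|
| G1 - G2: -0.06 | -1.8 to 1.7 | -2.7 to 2.6 | -3.1 to 3.0 |
| G1 - G3: 3.95 | 1.8 to 6.1 | 0.4 to 7.5 | -0.2 to 8.1 |
| G2 - G3: 4.01 | 2.3 to 5.7 | 0.9 to 7.2 | 0.2 to 7.8 |

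**Step 5. What no timing effect would look like.** If birth week is uncorrelated with cerclage week within a group, then corr(C, I) = -SD_C/SD_I:

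- Group 1: -(1.99 x 7)/41.27 = -0.34
- Group 2: -(2.97 x 7)/35.16 = -0.59
- Group 3: -(4.14 x 7)/49.35 = -0.59

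A clear negative association between placement week and interval is therefore expected with no effect of timing.

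**Step 6. Group 3 denominator.** 66.7% cannot arise from 35 patients (23/35 = 65.7%, 24/35 = 68.6%) but fits 22/33. With n = 33, the group 3 minus group 2 placement CI is -14.9 to 8.0 days, and G1 - G3 at r = 0 is 0.36 to 7.55 weeks. The conclusions do not change.

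**The case against.** **The sentence is only descriptive.** It has no causal verb and names no benefit, and prolongation of pregnancy is a listed outcome, so reporting the interval is legitimate. The interval should indeed stay, as a description. But the sentence is phrased as a general rule, and its position invites the benefit reading. Read literally, it only restates how the interval is defined.

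**Placement week was examined within groups.** The Results say cerclage week was evaluated against cerclage results in each group separately. No significant difference by cerclage week is reported for any group. This is a fair addition: it does not prove absence of an effect, but it gives the sentence no support.

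**The match is between point estimates, and only for groups 1 and 2.** This stands. The intervals in Step 4 are too wide to claim equal birth weeks, and against group 3 placement accounts for only part of the gap.

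**The benchmark correlation is idealised.** With normal distributions at the stated means and SDs, about 7.8% of group 3 births would precede their own cerclage. Excluding them moves -0.59 to about -0.53. The sign and the argument survive.

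**The damage is limited.** The Results are a short narrative, so birth weeks may be tabulated elsewhere. The plan's three named comparison outcomes are successful cerclage, good outcome and PPROM, and the sentence rests on none of them. This limits the scope of the point; it does not rescue the conclusion.

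**Conclusion.** The concern holds. The stated conclusion is drawn from an interval that contains placement week by construction. For groups 1 and 2, the 49.2-day longer interval goes with a 49.6-day earlier stitch, leaving implied mean birth weeks of 34.9 and 35.0. The reported figures neither support nor exclude an effect of timing, because the groups are defined by indication and the birth-week difference is known only to within about 1.8 to 3.1 weeks either way, depending on r.

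This rests on two assumptions: that the reported means cover the same patients, and that r lies between -0.8 and +0.5. The implied means and the G1 - G2 remainder do not depend on r. The contrasts of groups 1 and 2 with group 3 on successful cerclage and good outcome are not affected. The point should be fixed, because it changes what the study can conclude about timing.

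**What to change.** 1. Withdraw the sentence, or replace it with: *The interval from cerclage to birth starts at cerclage and therefore depends on cerclage week; it does not show an effect of timing.*
2. Report week of birth by group, with the planned ANOVA or Kruskal-Wallis test and pairwise differences with 95% CIs. Keep the interval as descriptive.
3. State that the groups differ by indication, so the between-group comparison is confounded and cannot test timing.
4. If a timing statement is still wanted, base it on an analysis labelled exploratory: gestational age at birth regressed on cerclage week within each indication group, giving the slope and 95% CI. Note that a birth cannot precede its own cerclage. Report it beside the within-group comparisons by cerclage week already made.

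The cost of items 1 to 3 is one replaced sentence, one statement on confounding, and one comparison with its pairwise differences on a variable already collected; no new data are needed. Item 4 would be imprecise. With no timing effect, the slope's SE is SD_I·sqrt(1 - r²)/(SD_C·sqrt(n - 2)), with both SDs in weeks and r from Step 5. This gives 0.509, 0.176 and 0.240, so 95% CI half-widths are about 1.0, 0.35 and 0.5 weeks of birth per week of cerclage in groups 1, 2 and 3.
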